## 5.2 Discontinuation of Subjects

If the investigator site identifies a subject who did not meet eligibility criteria but was inadvertently randomized, the sponsor-designated medical monitor must be contacted.

If the sponsor or designee identifies a subject who did not meet enrollment criteria and who was inadvertently randomized, the investigator site will be notified. A discussion must occur between the sponsor-designated medical monitor and the investigator to determine whether the subject may continue in the study. Inadvertently randomized subjects may be maintained in the study when the sponsor agrees with the investigator that it is medically appropriate for that subject. The investigator must obtain documented approval from the sponsor to allow the inadvertently enrolled subject to continue in the study.

A subject will be discontinued from the study in the following circumstances:

- The subject requests to be withdrawn from the study.
- The subject is permanently discontinued from study drug (see section [5.1.2](#)).
- The subject misses more than four doses of study drug over the course of the study, or misses two consecutive doses of study drug during the dose escalation phase.
- Enrollment in any other interventional clinical trial.
- The sponsor stops the study or stops the subject's participation in the trial for medical, safety, regulatory or other reasons consistent with applicable laws, regulations and good clinical practice (GCP).

- The investigator decides it is in the best interests of the subject not to continue in the study.
- The subject and/or blinded study staff become unblinded to the subject's treatment assignment.
- Any medication for weight loss is given for more than one week.
- If the subject, for any reason requires treatment for greater than one week with another therapeutic agent that has been approved for treatment of diabetes. A change in dose of metformin is not allowed, unless a temporary increase in dose is needed to treat hyperglycemia (see section 6.11). However, a change to an equivalent dose strength of metformin from immediate-release to extended-release (or vice versa) formulations is allowed.

Subjects discontinued from the study will be requested to complete an early termination (ET) visit as soon as possible (section 9.5). Subjects will be requested to complete a follow-up visit (see section 9.5) four weeks after their final dose.

### **5.3 Discontinuation of Study Sites**

Study site participation may be discontinued if the sponsor or its designee, the investigator, or the institutional review board (IRB) of the study site judges it necessary for medical, safety, regulatory, or other reasons consistent with applicable laws, regulations, and GCP.

### **5.4 Discontinuation of the Study**

The study will be discontinued if the sponsor or its designee judges it necessary for medical, safety, regulatory, or other reasons consistent with applicable laws, regulations, and GCP.

## **6 STUDY TREATMENT(S)**

### **6.1 Randomization**

Subjects who meet all eligibility criteria will be randomized to treatment at visit 2 (day 1) via the Interactive Response Technology system (IRT). Randomization will be stratified using the following variables: screening HbA1c (<8.5%, ≥8.5%) and baseline BMI (<30, ≥30 kg/m^2). The randomization to the treatment arms will be 1.75:1 for the active and placebo groups, respectively. Following randomization, study drug will be dispensed in a double-blinded manner.

### **6.2 Description of Treatment(s)**

OPK-88003 and matching placebo are provided in single-use 2 mL glass vials with blue flip-off lid, an aluminum seal and a rubber stopper (septum).

### 6.2.1 *OPK-88003 Injection*

**Dosage form:** solution for SC injection

**Dose strength:** 70 mg/vial (extractable volume 1 mL)

**Description:** clear, colorless liquid

**Nonactive components:**

**Storage conditions:**

CCI

A large black rectangular redaction box covers the content of the 'Nonactive components' and 'Storage conditions' fields for the OPK-88003 Injection section.

### 6.2.2 *Placebo Injection*

**Dosage form:** solution for SC injection

**Dose strength:** 0 mg/vial (extractable volume 1 mL)

**Description:** clear, colorless liquid

**Nonactive components:**

**Storage conditions:**

CCI

A large black rectangular redaction box covers the content of the 'Nonactive components' and 'Storage conditions' fields for the Placebo Injection section.

## 6.3 **Packaging and Labeling**

Vials of OPK-88003 and placebo will be supplied in cartons, each containing four vials, each for single use. Vials and cartons will be labeled according to regulatory requirements. The labels will include protocol number, sponsor name, investigational statement, storage conditions and instructions for use.

## 6.4 **Storage and Accountability**

While at the study site, vials will be stored frozen at  $-20 \pm 5^{\circ}\text{C}$  in the supplied packaging until assigned to a subject by IRT, and thereafter refrigerated ( $2-8^{\circ}\text{C}$ ) with access granted to authorized personnel only.

All sites must ensure that study drug has been kept under required conditions prior to dispensing. A temperature log recording the daily study drug storage conditions will be

maintained at each site. If temperature excursions occur during shipping or storage at site, study drug should not be dispensed, and the investigator or designee should contact the sponsor's designee as soon as possible for further instruction.

Once study drug is dispensed the subject will be instructed to transport the vials in the provided cool container and store refrigerated at home. Subjects will be instructed to return all used and unused vials in cool bags to the study site for study drug accountability.

The investigator or their designee(s) will maintain study drug accountability records throughout the course of the study from receipt of study drug until final reconciliation and return to the sponsor. Specifically, the investigator or their designee will confirm that all study drugs and supplies are received intact and in the correct amounts per the shipping forms. A study drug accountability and dispensing log will be maintained on site to record the study drug dispensed to subjects, including dates, quantity received and returned vial numbers. The investigator should ensure that the study drug is used only in accordance with the protocol.

The sponsor's designee will routinely verify the inventory of study drug supplies throughout the course of the study. All used and unused cartons/vials of study drug are to be retained at the site until the sponsor's designee has performed a complete verification.

Any discrepancies identified will be indicated with a specific explanation of each discrepancy. The investigator (or designee) must return all used and unused study drug in accordance with the sponsor's instructions, and a copy of the clinical supplies return documentation will be returned to the sponsor or designee. Drug accountability records, clinical drug supply receipts, and returns must be maintained by the investigator.

## **6.5 Treatments Administered**

This trial will evaluate 20 mg and 40 mg dose escalation and 70 mg target dose of OPK-88003 QW over a 30-week treatment period. Treatment allocation will be assigned by the IRT. The group randomized to OPK-88003 will initially receive 20 mg QW for four weeks, followed by 40 mg QW for four weeks. Once eight weeks of dose escalation are complete, subjects will receive a target dose of 70 mg QW OPK-88003 for 22 weeks. The control group will receive matched placebo SC injections QW for 30 weeks.

Site staff will train the subject on correct storage, preparation and administration of study drug, aiming for subject self-administration. The subject will administer the study drug at the study site visits as per schedule of events under supervision of an unblinded site personnel (eg, research nurse) to ensure injection technique is satisfactory. The subject will administer doses QW at home, with assistance if necessary.

Prior to injection, if the vial is frozen it should be allowed to thaw/equilibrate for a minimum of 1 hour and a maximum of 4 hours at room temperature. If the vial is refrigerated it should be allowed to equilibrate for a minimum of 30 minutes and a maximum of 4 hours at room temperature.

Detailed study drug handling and dosing instructions will be provided to support subject dosing.

All injections will be administered SC into the abdominal wall (or other sites if approved by the investigator). Instructions for rotation of injection sites and assessment of potential injection site reactions will also be provided.

The investigator or their designees are responsible for the following:

- explaining the correct use of the study drug to the subject
- verifying that instructions are followed properly
- maintaining accurate records of study drug dispensing and collection, and the return of all used and unused medication to the sponsor or designee at the end of the study

Subjects will be instructed to contact the investigator as soon as possible if they have any questions or issues concerning the injection of study drug or if they have any other study-related concerns so the issue/question can be assessed in a timely manner to ensure subject's safety.

All subjects should be observed for allergic reaction following study drug administration for at least 15 minutes at visits 2, 3, 4 and 5.

## **6.6 Materials and Supplies**

### **6.6.1 Study Drug Supplies**

Study drug cartons containing OPK-88003 or placebo for SC injection will be supplied to study sites. Ancillary supplies including needles and syringes will be provided separately. Study drug vials must always be stored in a secure location with access limited to designated study staff members.

### **6.6.2 Laboratory Supplies**

The sponsor or assigned designee will supply vacutainers, blood collection tubes, labels, boxes with labels for storage of serum and plasma samples and all necessary shipping supplies/containers, as specified in the laboratory manual. The investigator will supply centrifuge equipment. The investigator will ensure that all biohazard wastes are disposed of in accordance with investigator, site standard operating procedures (SOPs) and local regulations.

## **6.7 Selection and Timing of Dose for Each Subject**

There are no restrictions on the time of day each dose is administered, but it is advisable to administer the SC injections on the same day and time of the week. If a subject misses a dose on the scheduled day, then they should administer the dose as soon as possible and then

resume their regular schedule. Study drug should not be administered within four days of the previous injection.

## **6.8 Blinding**

OPK-88003 and placebo injections are identical in appearance in order to maintain a double-blind status. An unblinded site staff member will be available to support subject dosing as needed. Study drug will be managed using IRT. Each user will have a unique username and passcode to access the system. In case of an emergency, when knowledge of the treatment assignment for the subject is essential for the clinical management or welfare of the subject, the investigator may unblind the subject's treatment assignment. Prior to unblinding, the investigator should make every effort to contact the sponsor or designee before proceeding with the unblinding process, if possible. If a subject's treatment assignment is unblinded without sponsor or designee's prior knowledge, the sponsor must be notified immediately.

Each site will be provided with a sealed envelope containing a six-digit code that can be entered into the IRT to unblind a subject's treatment assignment. In order to preserve the double-blind of the study, a minimal number of sponsor personnel will have access to the randomization scheme and treatment assignments before the study is complete.

## **6.9 Concomitant Therapy**

Treatment with medications that are excluded in the entry criteria is not permitted.

The only concomitant anti-hyperglycemic medication permitted during this trial is metformin. Subjects treated with metformin upon entering this trial should remain on the same dose throughout the course of the trial, unless hyperglycemic criteria are met (see section 6.11). If a subject switches from the immediate-release formulation of metformin to the sustained-release formulation, the change will be on a milligram per milligram basis.

Doses of anti-hypertensive and lipid-lowering agents should remain stable during the study unless necessary to protect subject safety.

Doses of other prescription medications (eg, thyroxine, estrogen or progesterone replacement, selective estrogen receptor modulators) for treatment of concurrent medical conditions should remain stable during the study whenever possible.

Anti-emetic drugs that do not increase QTc (eg, cyclizine, meclizine) may be used to treat nausea and vomiting, but they should not be used prophylactically.

Non-steroidal anti-inflammatory medications (including aspirin and acetaminophen), cough suppressants, antihistamines, vitamin/mineral supplements, antibiotics and topical ointments may be used and are not restricted by the stable dosing requirements listed above.

If the need for additional concomitant medication arises, inclusion or continuation of the subject may be at the discretion of the investigator after consultation with the sponsor or their

designated medical monitor. Any additional medication used during the course of the study must be documented.

## 6.10 Restrictions

**Meals** – Subjects shall fast for at least 8 hours overnight prior to each visit where fasting labs are drawn or **CCI** measurements are taken.

**Alcohol** – Alcohol will not be permitted at least 8 hours prior to the study visit.

**Blood donation** – Study subjects should be instructed not to donate blood or blood products during the study and for 8 weeks following study completion.

**Contraception** – Male subjects or their female partners of child-bearing potential must use reliable contraception during intercourse throughout the treatment period and for three months after the last dose of study drug (as the risk of OPK-88003 to the unborn fetus is unknown). Females must not be of childbearing potential due to surgical sterilization (hysterectomy, bilateral oophorectomy or tubal ligation) or menopause.

Acceptable contraception includes male sterilization (with the appropriate post-vasectomy documentation of the absence of sperm in the ejaculate), oral, injected or implanted hormonal methods of contraception, intrauterine device or implant, and barrier methods of contraception (condom or occlusive cap, diaphragm or cervical/vault caps) with spermicidal foam/gel/film/cream/suppository. The use of barrier contraceptives should always be supplemented with the use of a spermicide.

## 6.11 Evaluation and Treatment of Hyperglycemia

Routine fasting (at least 8 hours) SMBGs and central laboratory FPG values will be used to determine the requirement for additional medication. If any fasting SMBG value exceeds the specified limit (Table 1), the subject will be instructed to contact the investigational site and asked to perform fasting SMBG on three consecutive days (see section 7.5).

If fasting SMBG values exceed the specified limit for three consecutive days, an unscheduled visit should be performed to assess FPG by the central laboratory.

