**Table 1 Threshold Glucose Levels**

| Study Period       | Threshold value          |
|--------------------|--------------------------|
| Baseline to week 8 | >270 mg/dL (15 mmol/L)   |
| Week 8 to week 12  | >240 mg/dL (13.3 mmol/L) |
| Week 12 to week 30 | >200 mg/dL (11.1 mmol/L) |

Values must be recorded on three consecutive days

If the SMBG values are confirmed by central laboratory FPG measurement, then an additional therapeutic intervention should be considered at the discretion of the investigator

*Confidential*

for subjects who are fully compliant with the assigned therapeutic regimen, in the absence of any acute condition that raises blood glucose. Any subject who requires additional glucose-lowering therapy for more than one week should be discontinued (see section 5.2).

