#### **7.8.4 Sample Collection, Storage, and Shipping**

Collection, processing, storage and shipping procedures will be performed in accordance with the instructions provided by the central laboratory. Detailed instructions will be provided in the laboratory manual. Blood samples will be collected and analyzed for clinical laboratory CCI parameters.

Additional blood draws may be needed for unscheduled visits. Missed samples should be drawn whenever possible. The investigator will provide a temperature monitored space with limited access for the study drug and a -20°C or -70°C freezer space for serum and plasma aliquot storage.

Laboratory samples, including antibody and bioanalytical samples, may be stored according to applicable laws, regulatory requirements or laboratory certification standards.

CCI

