### **11.2.2 Analysis Populations**

The intent-to-treat (ITT) population is defined as all randomized subjects. Statistical analyses (including the primary analysis) will be conducted on the modified ITT (mITT) population. The mITT population is defined as all randomized subjects who received at least one dose of study drug and have at least one post-baseline measurement for the primary outcome.

The safety population is defined as all randomized subjects who have received at least one dose of study drug. All safety analyses will be performed on the safety population.

Some efficacy measures will also be analyzed on the per-protocol (PP) dataset. The per-protocol (PP) population is defined as all randomized subjects who were compliant with study drug and completed the protocol and is a subset of the mITT population and include subjects who meet the following additional criteria: The PP population will include all subjects in the mITT population who complete the 30-week, double-blind treatment period without any significant deviations from the protocol procedures. The PP population will be used to assess robustness of the primary analysis results. A final listing of all subjects to be excluded from the PP population will be completed prior to unblinding the study database.

No adjustments for multiplicity will be performed. All tests of treatment effects will be conducted at a two-sided alpha level of 0.05 and/or two-sided 95% confidence interval (CI), unless otherwise stated.

The baseline value used for the analyses will be the last scheduled baseline value obtained for each subject prior to first IP dose administration. Any measurements/events that occurred after the subject started rescue therapy will not be included in the efficacy analyses.

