5 ANALYSIS ENDPOINTS

5.1 Primary Efficacy Endpoint

The primary efficacy endpoint is absolute change in HbA1c from baseline to Week 30. If the Week 30 measurement is missing, the last valid post-baseline observation (last post-baseline observation carried forward [LOCF]) algorithm will be applied to impute the missing Week 30 value only for subjects that have discontinued early due to hyperglycemia (Week 30/LOCF_H). Otherwise, no imputation will be made for the missing Week 30 values.

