5.3 Additional Secondary Endpoints

- Absolute change in body weight from baseline to Week 30;
- Absolute change and percent (%) change in body weight from baseline to Weeks 4, 8, 12, 16, 22, 26, 30, and 34 without LOCF;
- Number and percent of subjects achieving $\geq 5\%$ weight loss at Weeks 4, 8, 12, 16, 22, 26, 30, and 34 without LOCF;
- Absolute change in FPG from baseline to Weeks 4, 8, 12, 16, 22, 26, 30/LOCF_H, and 34;
- Absolute change in HbA1c from baseline to Weeks 4, 8, 12, 22, 30/LOCF_H, and 34;
- Number and percent of subjects achieving HbA1c $\leq 6.5\%$ at Weeks 4, 8, 12, 22, 30/LOCF_H, and 34;
- Number and percent of subjects achieving HbA1c $< 7.0\%$ at Week 30/LOCF_H; and
- Number and percent of subjects achieving HbA1c $< 7.0\%$ at Weeks 4, 8, 12, 22, 30, and 34 without LOCF.

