6.2 Baseline, Endpoint, and Other Statistical Considerations

The clinical statistical efficacy and safety analyses will be performed by Medpace.

First dose of study drug refers to the first dose of blinded study drug (Week 0 Day 1).

Baseline will be the measurement at Week 0 Day 1. If missing, the last valid measurement prior to the first administration of study drug will be used as baseline.

Any measurements/events that occur after the subject started rescue therapy will not be included in the efficacy analyses.

Unless specified otherwise, treatment groups will be OPK-88003 and placebo for summaries and analyses. Additional explorations may be done by OPK-88003 dose.

Descriptive statistics (n, mean, standard deviation, median, minimum, and maximum) will be used to summarize the continuous efficacy and safety data by treatment group. The count and frequency will be used to tabulate categorical measurements.

Data will be used as it is reported. LOCF may be used when specified. The value must be collected within the last dose date +10, inclusive, in order to be used as LOCF. Where specified, LOCF_H (for subjects that have discontinued early due to hyperglycemia) or LOCF_{All} (for all subjects) may be used.

No adjustments for multiplicity will be performed. All tests of treatment effects will be conducted at a two-sided alpha level of 0.05 and/or two-sided 95% confidence interval (CI), unless otherwise stated.

Analysis Visit Windows

For all efficacy and safety assessments, analysis visits will be assigned according to the actual study day, calculated as the assessment date – first dose date for assessments prior to the first dose date and assessment date – first dose date +1 for assessments on or after the first dose date. The analysis visit windows will be defined as the halfway point between the target visit days:

Analysis Visit	Target Visit Day	Analysis Visit Window (Days)
Visit 1 (Screening)	N/A	N/A
Baseline	1	≤ 1
Visit 3 (Week 1)	8	2 – 18
Visit 4 (Week 4)	29	19 – 43
Visit 5 (Week 8)	57	44 – 60

Analysis Visit	Target Visit Day	Analysis Visit Window (Days)
Visit 6 (Week 9)	64	61 – 67
Visit 7 (Week 10)	71	68 – 74
Visit 8 (Week 11)	78	75 – 81
Visit 9 (Week 12)	85	82 – 99
Visit 10 (Week 16)	113	100 – 134
Visit 11 (Week 22)	155	135 – 169
Visit 12 (Week 26)	183	170 – 197
Visit 13 (Week 30)	211	198 to \leq last dose date + 10
Visit 14 (Week 34/Follow-up)	239	N/A

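### HbA1c is not required at the hyperglycaemia visit, so if rescue starts before the early termination visit, LOCF_H can carry a Week 30 value nominally up to 10 weeks old at rescue

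*Protocol*

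**What the plan says.** **Hyperglycaemia pathway.** Under Protocol 6.11, a fasting self-monitored value above the Table 1 limit leads to three consecutive daily checks. If all exceed the limit, "an unscheduled visit should be performed to assess FPG by the central laboratory". If that FPG confirms, the investigator may consider additional therapy. The text after Table 1 adds: "Any subject who requires additional glucose-lowering therapy for more than one week should be discontinued". Protocol 5.2 then says: "Subjects discontinued from the study will be requested to complete an early termination (ET) visit as soon as possible". HbA1c is on the ET list (Protocol 9.5 and Schedule of Events).

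**Extra samples.** Protocol 7.8.4 says: "Additional blood draws may be needed for unscheduled visits". It names no analyte and requires none.

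**Data after rescue.** SAP 6.2 says: "Any measurements/events that occur after the subject started rescue therapy will not be included in the efficacy analyses". Protocol 11.2.2 has the same rule.

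**Imputation.** In SAP 5.1, a missing Week 30 HbA1c is filled with the last valid post-baseline value "only for subjects that have discontinued early due to hyperglycemia". SAP 6.2 requires a carried value to fall no later than 10 days after the last dose. It sets no maximum age.

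**HbA1c schedule.** SAP 5.3 lists "Absolute change in HbA1c from baseline to Weeks 4, 8, 12, 22, 30/LOCF_H, and 34", which agrees with the Schedule of Events. Weeks 16 and 26 have fasting glucose but no HbA1c.

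**mITT.** SAP 6.3.2 requires at least one valid post-baseline measurement of the primary outcome.

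**The concern.** LOCF_H is the only imputation in the primary analysis. SAP 8.2 keeps it as a deliberate exception when the analysis moves to MMRM, and its evident purpose is that subjects who fail glycaemically still contribute a Week 30 result. The quality of that result depends on which HbA1c is the last usable one.

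The plan brings these subjects in for a central-laboratory sample at the moment of failure, but does not require the primary endpoint to be measured on it. If rescue then starts before ET, the next HbA1c is unusable and an older value stands in for Week 30. Where glucose rose after that older value was taken, the subject enters the analysis looking better controlled than at failure. If such failures are commoner on placebo, the contrast would tend to shrink. A subject rescued before the Week 4 sample may have nothing to carry and would leave the mITT population, so LOCF_H could not retain that failure at all.

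**Working it through.** **1. Does the chain hold?**

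| Link | Source | Status |
|---|---|---|
| Unscheduled visit requires central FPG; HbA1c not named | Protocol 6.11 | Stated |
| Further draws possible | Protocol 7.8.4 | Permitted, not required |
| ET follows discontinuation and includes HbA1c | Protocol 5.2, 9.5 | Stated |
| First rescue dose precedes ET | Protocol 6.11, 5.2 | Possible, not stated |
| Values after rescue excluded | Protocol 11.2.2, SAP 6.2 | Stated |
| Last valid value carried, no maximum age | SAP 5.1, 6.2 | Stated |

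Every link is stated except the order of rescue and ET, so the conclusion is conditional on that order.

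**2. Age of the carried value at rescue.** The plan gives no figure for this. The greatest age is the interval between consecutive HbA1c visits. Nominal days are 1, 29, 57, 85, 155 and 211. Windows are ±2 days at Weeks 4, 8 and 12, and ±4 days at Weeks 22 and 30.

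| Interval | Nominal gap | Gap at window limits |
|---|---|---|
| Week 0-4 | 28 days; no post-baseline value yet | 30 days |
| Week 4-8 | 28 days (4 weeks) | 32 days (4.6 weeks) |
| Week 8-12 | 28 days (4 weeks) | 32 days (4.6 weeks) |
| Week 12-22 | 155 - 85 = 70 days (10 weeks) | 159 - 83 = 76 days (10.9 weeks) |
| Week 22-30 | 211 - 155 = 56 days (8 weeks) | 215 - 151 = 64 days (9.1 weeks) |

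These are maxima with all visits attended. A missed HbA1c visit lengthens them.

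**3. Can the effect on the contrast be derived?** No. The documents give neither the proportion leaving for hyperglycaemia nor the HbA1c change between the last scheduled visit and rescue. The following is illustration only.

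First, the plan's own power. Inputs from Protocol 11.1: 48 active, 27 placebo, difference 0.8, SD 1.0, two-sided alpha 0.05.
- Standard error = 1.0 × √(1/48 + 1/27) = 0.2406.
- Noncentrality = 0.8 / 0.2406 = 3.33 on 73 degrees of freedom.
- Power = 90.7% (t) or 91.4% (normal). The stated figure of at least 90% reproduces.

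Then the shift in the placebo mean = share carried × understatement. Assumed: share 5-15% of placebo, understatement 0.3-1.0 point, no carried values on active, and a simple comparison of means in place of the MMRM.
- Low: 0.05 × 0.3 = 0.015 point; difference 0.785; power 89.6%.
- High: 0.15 × 1.0 = 0.15 point; difference 0.65; power 76.0%.

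The low end is negligible and the high end is not. Nothing in the documents says where in the range the trial would fall.

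**The case against.** A reader might infer several stronger things, and the case against each has force.

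**That the ET HbA1c normally comes after rescue.** The discontinuation rule refers to a subject who requires therapy for more than a week. It does not say that a week must first be given. A site could judge the need to be lasting, stop participation and hold ET before any rescue dose. That HbA1c would be usable if taken within 10 days of the last dose. Neither document defines rescue therapy, so it is also unclear whether a temporary metformin increase triggers the exclusion. This objection stands: the order is possible, not established.

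**That HbA1c is not drawn at the visit.** Protocol 7.8.4 allows additional draws. What is missing is a requirement.

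**That the carried value always predates a deterioration.** Table 1 lowers the limit from above 270 to above 240 mg/dL at Week 8, and to above 200 at Week 12. HbA1c is drawn at both visits. A subject holding steady at 210 mg/dL becomes a failure after Week 12 without worsening, and the Week 12 HbA1c then represents that subject well. This stands, and it means that 10 weeks is an extreme and not a typical age.

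**That FPG and HbA1c would be carried from different dates in the same subject.** This assumes that unscheduled values already qualify for LOCF_H. If they do, the SAP change for HbA1c is clarification only; if they do not, the mismatch does not arise in this way. Different dates are in any case built into the schedule, since FPG is drawn at Weeks 16 and 26 and HbA1c is not.

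What remains is the conditional gap: no HbA1c is guaranteed at failure, and no limit is placed on the age of the value that replaces it.

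**Conclusion.** The point holds as a cheap improvement, with moderate confidence. If rescue starts before ET, the primary endpoint for a hyperglycaemia discontinuation rests on the last scheduled HbA1c. At rescue that value is nominally up to 10 weeks old (Weeks 12-22) or 8 weeks old (Weeks 22-30). Before Week 4 there may be no valid value, and the subject may leave the mITT population.

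A reader might go further and conclude that LOCF_H flatters placebo by a known amount. The documents do not support that. Shrinkage of the contrast requires that failures be commoner on placebo and that HbA1c rise between the last visit and rescue, and the documents quantify neither. The range of 0.015 to 0.15 point rests wholly on the assumptions shown. Nor does the point disturb the sample size calculation, whose stated power reproduces. Text following the primary model in SAP 6.9.1 is redacted, so any sensitivity analysis described there could not be assessed.

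**What to change.** - **Protocol 6.11 and Schedule of Events:** add HbA1c to the central-laboratory sample at the unscheduled hyperglycaemia visit, drawn before any additional therapy starts.
- **SAP 5.1 and 6.2:** confirm that this off-schedule, pre-rescue HbA1c counts as the last valid post-baseline observation for LOCF_H and for mITT membership. The same sentence would cover any such value that sites have already drawn under Protocol 7.8.4.

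The carried value would then date from the hyperglycaemia visit, and a subject who fails before Week 4 could stay in the mITT population. Glucose thresholds, rescue rules and the planned sample size do not change. The cost is one extra assay on an existing blood draw for the few subjects affected, an off-schedule record in the database, and two short text changes.
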